## **11.3 Sample Size and Power Analysis**

The original sample size in this study was 150 enrolled subjects. Additional proof testing and improvements in the device inspection process were employed during the study, at which time it was determined that an additional cohort of subjects was necessary. We are now comparing a cohort of subjects enrolled after these changes to the original cohort of subjects.

With an expected attrition rate of 10% per annum, this will yield an evaluable sample size of 52 shoulders at ten years ( $150 * 0.9^{10} = 52.3$ , where 0.9 or 90% is the number expected to be retained from one year to the next). Based on past experience, we may obtain clinical follow-up on this number of shoulders, but we may obtain radiographic follow-up on as few as two-thirds of these shoulders (about 35 shoulders). This remaining number of evaluable shoulders with clinical and radiographic follow-up is adequate to establish a reliable ten-year survival estimate of survival for hemi arthroplasty (Dorey and Amstutz, 1986).

For the new cohort, the sample size is calculated based on the non-inferiority of the study device. The success rate for the study device is 96.1% from the original population and is used as reference rate. Therefore, for a conservative success rate of 96.1% of the study device is used in the study. The non-inferiority margin  $\delta$  of -0.033 is chosen in the study. 212 subjects are required to achieve  $100(1 - \beta) \% = 80\%$  power to detect non-inferiority at the Significance level of  $\alpha = 0.05$ . To account for 10% lost to follow-up, the

total number of additional subjects is 237. Therefore, the estimated enrollment for the study will be 387 subjects.

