# 6 STATISTICAL CONSIDERATIONS

## 6.1 Determination of Sample Size

The following is the sample size justification taken from the study protocol V2, 27-May-2013:

The original sample size in this study was 150 enrolled subjects. Additional proof testing and improvements in the device inspection process were employed during the study, at which time it was determined that an additional cohort of subjects was necessary. We are now comparing a cohort of subjects enrolled after these changes to the original cohort of subjects.

With an expected attrition rate of 10% per annum, this will yield an evaluable sample size of 52 shoulders at ten years ( $150 * 0.9^{10} = 52.3$ , where 0.9 or 90% is the number expected to be retained from one year to the next). Based on past experience, we may obtain clinical follow-up on this number of shoulders, but we may obtain radiographic follow-up on as few as two-thirds of these shoulders (about 35 shoulders). This remaining number of evaluable shoulders with clinical and radiographic follow-up is adequate to establish a reliable ten-year survival estimate of survival for hemi arthroplasty (Dorey and Amstutz, 1986).

For the new cohort, the sample size is calculated based on the non-inferiority of the study device. The success rate for the study device is 96.1% from the original population and is used as reference rate. Therefore, for a conservative success rate of 96.1% of the study device is used in the study. The non-inferiority margin  $\delta$  of -0.033 is chosen in the study. 212 subjects are required to achieve  $100(1 - \beta) \% = 80\%$  power to detect non-inferiority at the Significance level of  $\alpha = 0.05$ . To account for 10% lost to follow-up, the total number of additional subjects is 237. Therefore, the estimated enrolment for the study will be 387 subjects.

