## 7.2 Analysis Populations

The following subject populations will be used for the statistical analysis of this study.

- **Full analysis set population (FAS)**, following Intention to Treat principle including all subjects who are enrolled into the study.
- **Per-Protocol Population (PP)**, including all subjects in the full analysis set who have no significant protocol deviations and met the inclusion/exclusion criteria.
- **Per-Protocol Population 1(PP1)**, including all subjects in the full analysis set who have no significant protocol deviations and met the inclusion/exclusion criteria. This is the original cohort of subjects in the study who were enrolled prior to the additional proof testing and improvements in device inspection process. This population will be used for supporting analysis of the primary endpoint.
- **Per-Protocol Population 2(PP2)**, including all subjects in the full analysis set who have no significant protocol deviations and met the inclusion/exclusion criteria. This is the additional cohort of subjects who were enrolled after the additional proof testing and improvements in device inspection process. This population will be used for supporting analysis of the primary endpoint.

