### 7.9 Analysis of Primary Endpoint(s)

A composite endpoint for Clinical success (device survival) is defined as a binary variable (1/0) (1 if all the following are true and 0 if any is false):

- A. Device remains implanted.
- B. Absence of device-related complications requiring surgical replacement, removal, or augmentation of components.
- C. Freedom from chronic dislocation.

The primary endpoint is the clinical success (device survival) rate at 10-years.

The study hypothesis is to test whether the 10-year survival (i.e., clinical success) rate in the investigational PyroTITAN HRA group is non-inferior to the reference rate at 96.1%. This study will be considered successful if the upper bound of the two-sided 95% confidence interval for the success rate difference (reference – study survival rate) is less than the non-inferiority margin of 3.3%.

The primary non-inferiority hypothesis is formulated as:

$$H_0: P_0 - \delta \geq P_T$$

$$H_a: P_0 - \delta < P_T$$

The variables are defined as follows:

$P_T$  = 120-month success rate in the PyroTitan HRA group

$P_0$  = Reference success rate from original population

$H_0$  = Null hypothesis

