## Statistical Analysis Plan

A Multi-center Outcomes Clinical Study of the PyroTITAN™ HRA Shoulder Implant in Humeral Head Resurfacing

Number: CP-HRA-002  
ST: ST1159  
Version: 1.0 05/Oct/2023  
Page: 15 of 19

$H_a$  = Alternative hypothesis that the success rate in the investigational group is non-inferior to the reference rate

$\delta$  = Non-inferiority margin pre-specified to be 3.3%.

The survival rate (the clinical success rate) will be calculated and the associated 95% exact confidence interval presented. If the upper 95% confidence limit is greater than the reference rate minus the non-inferiority margin ( $96.1 - 3.3 = 92.8\%$ ) then non-inferiority of the observed rate to the reference rate to within a 3.3% margin can be concluded.

Additionally, survival rate (the clinical success rate) and the associated 95% exact confidence interval at 2 and 5 years will be calculated and presented.

If data allows, time-to-event curves for device survival will be estimated using the Kaplan-Meier technique. For analysis of device survival, those lost to follow up or withdrawn from the study for reasons other than device revision or removal will be regarded as censored observations.

The primary analysis of this endpoint is to be carried out using the FAS population. The same analysis will be carried out on the PP population as supporting analyses.

As an additional analysis, the primary endpoint will be summarised for PP1 and PP2 populations in order to compare the cohort of subjects enrolled after the device changes to the original cohort of subjects.

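### The non-inferiority test was sized for the post-change cohort, but SAP 7.9 runs it on all enrolled subjects, including the cohort that supplied the 96.1% reference

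*SAP*

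**What the plan says.** Protocol 11.3, repeated in SAP 6.1, describes an original cohort of 150 and an additional cohort enrolled after extra proof testing and changes to device inspection. It states the purpose as "We are now comparing a cohort of subjects enrolled after these changes to the original cohort of subjects", and adds "For the new cohort, the sample size is calculated based on the non-inferiority of the study device". The benchmark is internal: "The success rate for the study device is 96.1% from the original population and is used as reference rate". With a margin of 3.3 points, 212 subjects are said to give 80% power at α = 0.05. This is inflated to 237 for 10% loss, so total enrolment is 150 + 237 = 387.

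SAP 7.9 defines P_0 as "Reference success rate from original population" and P_T as the 120-month rate in the PyroTITAN group, without limiting P_T to either cohort. The decision rule begins "This study will be considered successful if the upper bound of the two-sided 95% confidence interval for the success rate difference" and requires that bound, for reference minus study rate, to be below 3.3%. On the analysis set, "The primary analysis of this endpoint is to be carried out using the FAS population"; SAP 7.2 defines the FAS as "including all subjects who are enrolled into the study".

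The two cohorts appear separately only as PP1 and PP2. SAP 7.2 gives these a supporting role, and SAP 7.9 says "the primary endpoint will be summarised for PP1 and PP2 populations in order to compare the cohort of subjects enrolled after the device changes" with the original one. No test or criterion is attached. SAP 7.4 flags PP1 and PP2 but has no cohort flag within the FAS.

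**The concern.** The sample-size section and the success rule address different populations. The first asks whether devices implanted after the change do as well as those implanted before. The second asks whether all devices together meet a benchmark that came from part of the same group. The new cohort can then pass or fail because of how the original cohort fares at ten years, and no decision rule applies to the new cohort alone.

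The benchmark adds a second difficulty. SAP 7.9 treats 96.1% as a known constant for a 120-month rate, but neither document says when it was measured, in how many subjects, or with what precision. If it is not a 10-year rate, a fail at 120 months could reflect the benchmark rather than the device.

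**Working it through.** **1. Reproduce the sample size.** Inputs from Protocol 11.3: p = 0.961, margin 0.033, power 80%, α = 0.05 (sidedness not stated). One-sample normal approximation against a fixed reference, one-sided 0.05:

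n = (1.645 + 0.842)² × 0.961 × 0.039 / 0.033² = 212.8.

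This matches the stated 212. Then 213 / 0.9 = 236.7, rounded up to 237, and 150 + 237 = 387. Other versions do not match: one-sided 0.025 gives 271, the null variance gives 318, and a two-sample test gives 426 per arm. The arithmetic therefore confirms the text: one cohort of new subjects, with the reference taken as error-free.

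**2. Composition of the FAS.** The original cohort's planned share is 150 / 387 = 38.8%.

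**3. What pooling does to the threshold.** With a fixed reference, the difference rule means that the lower limit for the study rate must exceed 96.1 − 3.3 = 92.8%. The new-cohort rate at which the pooled rate equals 92.8% is (0.928 × 387 − 150 × p₁) / 237, where p₁ is the original cohort's 10-year rate.
- p₁ = 96.1%: 90.7%, an effective margin of 5.4 points.
- p₁ = 89.3%: 95.0%, an effective margin of 1.1 points.

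**4. Illustrative values of p₁.** It is unknown. Under a constant hazard, 96.1% at 3.5 years extrapolates to 0.961^(10/3.5) = 89.3% at ten years, and 96.1% at 2 years to 0.961^(10/2) = 82.0%. These are illustrations, not bounds.

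**5. Chance of passing.** Exact binomial calculation; pass if the lower exact two-sided 95% limit exceeds 92.8%. Evaluable numbers with 10% yearly attrition are 150 × 0.9¹⁰ ≈ 52 (the protocol's figure) and 237 × 0.9¹⁰ ≈ 83 (an assumption, since the protocol states yearly attrition only for the original 150). The pass marks are 132/135 pooled and 82/83 alone. With no loss they are 370/387 and 228/237.

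| Evaluable (original + new) | True new-cohort rate | New alone | Pooled, p₁ = 96.1% | Pooled, p₁ = 89.3% | Pooled, p₁ = 82.0% |
|---|---|---|---|---|---|
| 52 + 83 | 92.8% | 1.5% | 3.8% | 0.2% | 0.01% |
| 52 + 83 | 96.1% | 16% | 22% | 2% | 0.1% |
| 150 + 237 (no loss, best case) | 92.8% | 2.2% | 11.8% | 0.1% | <0.01% |
| 150 + 237 (no loss, best case) | 96.1% | 55% | 74% | 5% | 0.01% |

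Where both cohorts are at 96.1% (74% against 55%, and 22% against 16%), the gap is sample size only and not distortion. If both are at 89.3%, every pass chance is below 0.1%, so the choice of set makes no practical difference.

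**6. The benchmark.** The 96.1% already stands in the protocol dated 27 May 2013. Protocol 12.0 gives the CE mark as 30 November 2009, about 3.5 years before. If implantation followed the CE mark (an assumption), 96.1% cannot be an observed 10-year rate. It is also not a simple proportion of 150: 144/150 = 96.0% and 145/150 = 96.7%.

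**The case against.** The best defence is that pooling is a legitimate choice. The primary objective in SAP 4.1 concerns the prosthesis, not one cohort. The design is non-comparative, P_T is written for the whole device group, and Protocol 11.1 calls the study exploratory. The cohort comparison is also not dropped, because SAP 7.2 and 7.9 keep it as supporting work. This stands as a reason to report the pooled rate. It does not make the pooled test the one that was sized, nor does it explain a P_T that includes the cohort defining P_0. The PP1/PP2 summary is per-protocol and has no criterion.

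Three stronger readings are tempting and should not be adopted.
- A reader might infer that pooling makes success easier. It does so only if the original cohort holds up at ten years; otherwise it makes success harder. The 11.8% is also not an error rate for the pooled hypothesis: at p₁ = 96.1% and a new cohort at 92.8%, the pooled rate is (150 × 0.961 + 237 × 0.928) / 387 = 94.1%, which is above the threshold.
- A reader might infer that the SAP silently departs from a protocol-specified analysis and should have listed this in SAP 7.14. Protocol 11.6 to 11.9 name no primary analysis set and no non-inferiority analysis; only the sizing text points to the new cohort.
- A reader might infer that 96.1% is known to be an early rate. The documents give no time point; the dating rests on the CE-mark assumption.

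**Conclusion.** The mismatch is real and should be fixed. The success rule in SAP 7.9 does not test the cohort for which 212 and 237 were calculated, and 39% of its planned sample is the cohort behind the reference. The direction of the effect on the new cohort's result is unknown. Under the protocol's attrition applied to both cohorts, a new cohort at 92.8% passes 0.01% to 3.8% of the time pooled, against 1.5% alone, across the three illustrated original-cohort rates. With no loss the range is below 0.01% to 11.8%, against 2.2%.

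These figures rest on planned cohort sizes, simple binomial outcomes among evaluable subjects, and use of the lower limit as the difference rule implies. SAP 7.9 also contains a sentence that compares the upper limit with 92.8%; that is a separate defect.

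The unstated time point, denominator and precision of 96.1% form a second gap. It would remain whichever population is tested.

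**What to change.** In SAP 7.9, apply the 92.8% criterion, using the lower limit so that it agrees with the difference rule, to FAS subjects enrolled after the proof-testing and inspection change. Add a FAS cohort flag in SAP 7.4. Report the pooled FAS rate and the original-cohort rate with exact 95% intervals for the overall device objective.

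If the sponsor prefers to keep the pooled FAS as primary, the SAP should say so with a reason, restate the power for that set, and show the new-cohort FAS result against 92.8% beside it.

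In either case:
- State the source, follow-up time and denominator of 96.1%. If it is not a 10-year rate, state that the 120-month comparison is not like-for-like.
- Restate the new-cohort power under the exact two-sided 95% limit. At a true rate of 96.1% it is 41% with 212 evaluable, 55% with 237 and 16% with 83.
- Record the change and whether it was made before any interim or 10-year results were seen. The study is open and SAP 6.3 plans a 5-year interim analysis, so an undated change could look data-driven.

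The cost is wording, one flag and one table; no new data are needed. The drawback is a wider interval and less power than pooling if the original cohort holds up: with both cohorts at 96.1%, 55% instead of 74% with no loss, or 16% instead of 22% at 52 + 83.

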## 7.10 Analysis of Secondary Endpoint(s)

### ASES

ASES Scores range from 0 to 100 with a score of 0 indicating a worse shoulder condition and 100 indicating a better shoulder condition.

ASES questionnaires that are incomplete for the questions used for scoring at the baseline visit will not be included in the analyses.

The ASES score will be derived for each patient at each visit and summary statistics will be presented. Change from baseline score to each post-operative visit will also be presented. A paired sample t-test will be used to test changes in the scores from baseline to each post-operative visit. If the t-test assumptions are not met then a Wilcoxon Signed Rank test will be considered.

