## **7.0 Revision/Re-operation**

---

Post-operative surgical procedures associated with the operative shoulder are categorized as Adverse Events. If a Subject undergoes any surgical procedure on the operative shoulder in which all of the original Pyro-Titan Resurfacing Shoulder implant components are retained (debridement etc), the Subject is not withdrawn from the study and all follow-up visits are maintained according to the Subject Management Schedule. If the Pyro-Titan Resurfacing Shoulder prosthesis implant is removed then the Subject is considered revised, is withdrawn from the study, an Adverse Event and Study Completion CRFs must

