## 7.3 Handling of Missing, Incomplete and Repeat Data

Data will be analysed as observed in the study database.

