## WOOS

There are 19 questions, each question is answered on a visual analogue scale ranging from 0 to 100. The questions are divided into four domains: Physical symptoms (max score 600), sports and work (max score 500), lifestyle (max score 500) and emotions (max score 300). The overall score ranges from 0 to 1900, with 1900 being the worst. For ease of interpretation, scores are converted to a percentage of the maximum score for each domain and overall  $[(\text{score}/\text{max score}) * 100]$ .

The WOOS score for each domain and overall will be derived for each patient at each visit and summary statistics will be presented. Change from baseline scores per domain and overall to each post-operative visit will also be presented.

A paired sample t-test on the overall WOOS score will be used to test changes in the scores from baseline to each post-operative visit. If the t-test assumptions are not met then a Wilcoxon Signed Rank test will be considered.

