## EQ-5D Quality of Life Questionnaire

The EQ-5D-3L is a standardised measure of health status developed by the EuroQol Group and provides a simple measure of general health. The EQ-5D-3L descriptive system contains 5 dimensions: Mobility, Self-Care, Usual Activities, Pain/ Discomfort, Anxiety/ Depression. The subject is asked to answer a question on each dimension on a scale comprising of 3 levels: no problems (1), some problems (2), and extreme problems (3). This decision results in a 1-digit number expressing the level selected for that dimension. The digits for the 5 dimensions can be combined in the order shown above to form a 5-digit profile (i.e. 11111 describes no problems in any dimension). This can then be cross-referenced using vendor provided "EQ-5D-3L Crosswalk Index Value Calculator" against the country of the investigator site (Country code - site ID: AU - 401, 402; GB - 403; FR - 404; SE - 406) to come up with an index value describing the respondent's health state. Higher index values indicate better health and lower index values describe worse health.

The subject responses to each dimension (categorical) and the overall EQ-5D-3L index values (continuous) will be summarized at all study visits. The change in the index value between baseline and all post-baseline study visits will also be summarised.

EQ-5D-3L index value will be assessed using repeated measures ANCOVA model, with the change from baseline index value as the dependent variable. As a minimum the model will contain terms for visit (repeated term) and baseline index value. The following terms will be added to the model using a stepwise selection procedure with an F-value to attain a significance level of 0.1: site, primary diagnosis and BMI. The p-value for the type III effects of all fixed effects terms included in the final model will be presented. The Least Square Mean (LSMean) change in EQ-5D-3L index value between baseline and all post-baseline study visits will be presented with the associated 95% confidence interval and p-value.

If the data does not satisfy the assumptions of an ANCOVA model then an appropriate non-parametric analysis will be considered such as Wilcoxon Signed Rank Test, with the Hodges-Lehmann estimate of the median change in index value presented along with the associated 95% confidence interval.

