# Statistical Analysis Plan

A Multi-center Outcomes Clinical Study of the PyroTITAN™ HRA Shoulder Implant in Humeral Head Resurfacing

Number: CP-HRA-002  
ST: ST1159  
Version: 1.0 05/Oct/2023  
Page: 18 of 19

EQ VAS will be assessed using repeated measures ANCOVA model, with the change from baseline in EQ VAS as the dependent variable. As a minimum the model will contain terms for visit (repeated term) and baseline EQ VAS. The following terms will be added to the model using a stepwise selection procedure with an F-value to attain a significance level of 0.1: site, primary diagnosis and BMI. The p-value for the type III effects of all fixed effects terms included in the final model will be presented. The Least Square Mean (LSMean) change in EQ VAS between baseline and all post-baseline study visits will be presented with the associated 95% confidence interval and p-value.

If the data does not satisfy the assumptions of an ANCOVA model then an appropriate non-parametric analysis will be considered such as Wilcoxon Signed Rank Test, with the Hodges-Lehmann estimate of the median change in EQ VAS presented along with the associated 95% confidence interval.

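### Late mean changes in ASES, WOOS, Constant and VAS pain may be biased by attrition, because each visit is tested by a paired t-test on the subjects still observed; a likelihood-based repeated-measures model is a cheap improvement

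*SAP*

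**What the plan says.** **Shoulder scores (SAP 7.10).** For ASES: "A paired sample t-test will be used to test changes in the scores from baseline to each post-operative visit". VAS pain and Constant-Murley carry the same sentence. For WOOS: "A paired sample t-test on the overall WOOS score will be used to test changes in the scores from baseline" to each post-operative visit. A Wilcoxon signed-rank test is the fallback for ASES, WOOS and Constant; none is named for VAS pain.

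**Missing data (SAP 7.3).** "Data will be analysed as observed in the study database". There is no imputation rule and no missing-data sensitivity analysis for these scores.

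**EQ-5D and EQ VAS (SAP 7.10).** "EQ-5D-3L index value will be assessed using repeated measures ANCOVA model", and "EQ VAS will be assessed using repeated measures ANCOVA model". Both have change from baseline as the outcome, visit and baseline as minimum terms, and site, primary diagnosis and BMI offered by stepwise selection. Neither an estimation method nor a covariance structure is named.

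**Attrition (Protocol 11.3, repeated in SAP 6.1).** For the original 150 subjects: "With an expected attrition rate of 10% per annum", giving 52 shoulders at ten years. For the new cohort, 237 are enrolled to cover 10% lost to follow-up, with no time horizon given.

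**Who leaves (Protocol 6.5, 7.0, 8.0).** A subject whose implant is removed "is withdrawn from the study", and the remaining visits are not required. Other post-operative withdrawals need no further follow-up, but their data up to that time stay available. Subjects who refuse to return count among those lost to follow-up.

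**The concern.** Under these rules each paired test uses only subjects with both a baseline score and a score at that visit. A subject who leaves after year 4 contributes nothing to the 5-, 8- and 10-year results, although the earlier post-operative scores are kept. The mean change among those still observed equals the mean change in all subjects only if those lost would have changed by the same amount on average.

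At least one route out of follow-up, revision, is tied to outcome by design. The study has no control arm, and Protocol 11.2 says results will be contrasted with the literature. The absolute mean change is therefore the result, and selection cannot cancel between arms. SAP 7.14 adds the 5-year interim analysis so that the 2- and 5-year data can be published. The SAP gives no reason for handling the shoulder-specific scores more simply than the generic ones.

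**Working it through.** **1. The plan's own attrition figures.** Original cohort: 150 × 0.9^10 = 52.3, as stated. That is 34.9% retained and 65.1% missing at ten years; at five years 1 − 0.9^5 = 41% are missing. New cohort: 237 × 0.9 = 213.3, which covers the 212 required.

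**2. Two readings for the whole study at ten years.**
- 10% a year applied to all 387: 387 × 0.9^10 = 134.9 observed; share missing 0.651.
- Each cohort's own figure: 52.3 + 213.3 = 265.6 of 387 = 68.6% observed; share missing 0.314. This assumes that the new cohort's 10% covers the full ten years.

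**3. Bias of the observed-case mean change.** Bias = share missing × (mean change of those retained − mean change of those lost). The difference is not in the documents, so a range is shown, in points.

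| Difference | 10 y, 0.651 missing | 10 y, 0.314 missing | 5 y, 0.410 missing |
|---|---|---|---|
| 0 | 0 | 0 | 0 |
| 2 | 1.3 | 0.6 | 0.8 |
| 5 | 3.3 | 1.6 | 2.1 |
| 10 | 6.5 | 3.1 | 4.1 |
| 15 | 9.8 | 4.7 | 6.1 |

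A negative difference (good scorers leave) reverses the sign.

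**4. Revision as the only informative loss.** Assume 3.9% revised (100 − 96.1, the reference rate) to 7.2% (100 − 92.8, the reference minus the margin), with 20 to 40 points less gain. The overstatement runs from 0.039 × 20 = 0.8 to 0.072 × 40 = 2.9 points.

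**5. Simulation of both estimators.** All inputs except N, the visit times and the 10% yearly loss are assumptions: SD 20; mean 35 at baseline and 75 from one year on, so a true ten-year change of 40; higher is better, as for ASES and Constant (VAS pain and WOOS as scored here run the other way); post-operative correlation 0.7; N = 387; about 135 observed at ten years; 300 replicates. Slopes are on the logit scale per SD. The likelihood estimator uses all observed visits and lets the baseline slope differ by visit.

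| Dropout driven by | Baseline correlation | Paired change | Likelihood change |
|---|---|---|---|
| Poor previous observed score, slope 0.5 / 1.0 | 0.1 | 45.1 / 48.5 | 39.9 / 40.0 |
| same | 0.3 | 43.5 / 45.5 | 39.9 / 39.8 |
| same | 0.5 | 41.8 / 42.9 | 40.0 / 40.0 |
| Good previous observed score, slope 0.5 | 0.1 / 0.3 / 0.5 | 35.1 / 36.6 / 38.1 | 40.0 / 40.1 / 39.8 |
| Poor current, unobserved score, slope 0.5 / 1.0 | 0.1 | 45.6 / 49.9 | 41.2 / 42.7 |
| same | 0.3 | 44.2 / 47.0 | 41.4 / 42.8 |
| same | 0.5 | 42.3 / 44.0 | 41.3 / 42.6 |

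With one correlation of 0.6 across all visits, baseline included:
- Random loss: both estimators 40.0.
- Dropout on a poor previous score: paired 39.9 / 39.8, likelihood 40.0 / 40.0.
- Dropout on a poor unobserved score: paired 40.8 / 41.4, likelihood 41.5 / 43.1.

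So, when loss depends on observed scores, the likelihood estimate stays within 0.2 of the truth in either direction, while the paired estimate ranges from 4.9 too low to 8.5 too high. When loss depends on the unobserved score, the likelihood estimate is still 1.2 to 3.1 too high. It is usually closer than the paired estimate, but not in the equal-correlation case.

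**The case against.** The protocol calls the study exploratory and itself specifies t-tests or signed-rank tests of pre- against post-operative values (11.9), so the SAP follows its protocol. The four scores do not enter the success criterion, and failures are counted in the primary endpoint. Attendance per visit, reasons for completion and numbers of observations are reported (SAP 7.6, 7.1), so attrition will be visible. Against an assumed gain of 40 points, a bias of a few points would not reverse a finding of improvement. All of this stands, and it limits the point to a cheap improvement. It does not dispose of it, because the size of the change is what will be set beside the literature.

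The simulation also partly favours the model: dropout on the last observed score is the condition under which likelihood estimation works. The runs with dropout on the unobserved score show the limit.

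Three stronger readings are tempting, and the documents support none of them:
- *Late gains are overstated.* That requires those lost to have gained less than those retained. The documents give no dropout mechanism, SD, expected change or correlation for these scores. Nil and reversed bias are both possible.
- *The SAP already has the right model and need only copy it.* Repeated-measures ANCOVA is named for EQ-5D without an estimation method or covariance structure. A complete-case version would not help.
- *Only the estimator changes.* The SAP does not say what is to be estimated for revised subjects. A model that assumes data missing at random implicitly projects their scores as if the implant were still in place, so adopting it changes the target unless this is stated.

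**Conclusion.** The point holds as a risk, not as a demonstrated bias. Per-visit paired t-tests on subjects still observed leave late mean changes exposed to selective loss, and they ignore post-operative data that the plan keeps.

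If subjects with poor scores leave, the ten-year gain would probably be overstated, by roughly 2 to 8 points (1.8 to 8.5 in the runs with dropout on the previous observed score). This rests on the assumed SD of 20, the assumed correlations and 10% yearly dropout in all 387 subjects. The protocol states that rate for the original 150 only. With 10% total loss in the new cohort, the multiplier falls from 0.651 to 0.314, so the bias would be smaller; that case was not simulated. Revision alone gives about 0.8 to 2.9 points under the assumptions in step 4.

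This is a cheap improvement to secondary analyses. The primary success criterion is unaffected.

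**What to change.** In SAP 7.10, for ASES, overall WOOS, Constant and VAS pain:

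1. Make the main analysis a repeated-measures model of change from baseline fitted by REML, with visit, baseline and baseline-by-visit terms, unstructured covariance with a stated fallback if it does not converge, and all observed visits.
2. Report the LSMean change with 95% CI and the number observed at each visit.
3. Keep the paired t-test as a sensitivity analysis.
4. State that scores after implant removal are not observed, so the model estimate is hypothetical for revised subjects.
5. Add a simple missing-not-at-random sensitivity analysis, for example a delta adjustment for revised and lost subjects over a stated range.
6. List the change in SAP 7.14.

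The SAP's EQ-5D derivations (7.4) point to an LOCF rule in 7.3 that is not there; the new text should not inherit that reference.

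The cost is some SAP wording and programming, with no new data. The downside is slightly more modelling and less simple output than a paired test.
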